# 7.6.7 Immune-Mediated Adverse Events (US Submission)

IMAEs will be summarized by treatment group for each immune-mediated category / PT using the 100-day safety window:

- Overall summary of non-endocrine IMAEs by worst CTC grade (any grade, grade 3-4, grade 5) where immune modulating medication was initiated presented by Category / PT.
- Overall summary of endocrine IMAEs by worst CTC grade (any grade, grade 3-4, grade 5) presented by Category / PT.
- Overall summary of non-endocrine IMAEs leading to discontinuation by worst CTC grade (any grade, grade 3-4, grade 5) where immune modulating medication was initiated presented by Category / PT.
- Overall summary of endocrine IMAEs leading to discontinuation by worst CTC grade (any grade, grade 3-4, grade 5) presented by Category / PT.
- Overall summary of non-endocrine IMAEs leading to dose delay or reduction by worst CTC grade (any grade, grade 3-4, grade 5) where immune modulating medication was initiated presented by Category / PT
- Overall summary of endocrine IMAEs leading to dose delay or reduction by worst CTC grade (any grade, grade 3-4, grade 5) presented by Category / PT.
- Summaries of time-to onset and time-to resolution of non-endocrine IMAEs where immune modulating medication was initiated presented by Category.
- Summaries of time-to onset and time-to resolution of endocrine IMAEs presented by Category.

A by-subject listing of IMAEs will be provided. By-subject listings of time-to resolution for longest IMAEs cluster (any grade and grade 3-5 in separate summaries) will also be provided. For new studies which collect investigator assessment of potential IMAE data, a by-subject listing of AEs considered as immune-mediated events per investigator but not qualified for IMAEs definition will also be provided.

In addition, for all nivolumab treated subjects who experienced at least one IMAE, the following data presentation will be provided:

- Summary of subjects who were re-challenged with nivolumab by IMAE category, with extended follow-up
- Summary of subjects who were re-challenged with nivolumab or ipilimumab by IMAE category, with extended follow-up

For these, re-challenge is considered to have occurred when last nivolumab and/or ipilimumab infusion was administered after the onset of an IMAE.

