4.5.2.1 Nivolumab and Ipilimumab (Arm A)

Dose delay criteria apply for all drug-related AEs. Treatment delay is up to 6 weeks for nivolumab and up to 12 weeks for ipilimumab from the last dose are allowable (any dose delays greater than these will require approval from the medical monitor). It is permissible in cases of a dose held due to AE to skip the dose in the cycle in order to bring the patient back on track with the next Cycle visit.

Tumor assessments for all participants should continue as per protocol even if dosing is delayed.

Nivolumab and ipilimumab administration should be delayed for the following:

- Grade 2 non-skin, drug-related AE, with the exception of fatigue
- Grade 2 drug-related creatinine, AST, ALT and/or Total Bilirubin abnormalities
- Grade 3 skin, drug-related AE
- Grade 3 drug-related laboratory abnormality, with the following exceptions:
 - Grade 3 lymphopenia or asymptomatic amylase or lipase does not require dose delay
 - Grade ≥ 3 AST, ALT, Total Bilirubin will require dose discontinuation (see section 4.5.5)
- Any adverse event, laboratory abnormality, or intercurrent illness which, in the judgment of the investigator, warrants delaying the dose of study medication.
- Participants receiving ipilimumab in combination with nivolumab that have drug-related toxicities that meet the criteria for dose delay, should have both drugs (ipilimumab and nivolumab) delayed until retreatment criteria are met. (Exceptions apply to the retreatment criteria after dose delay of ipilimumab and nivolumab for Grade ≤ 3 amylase and lipase

abnormalities that are not associated with symptoms or clinical manifestations of pancreatitis and that are attributed to ipilimumab alone.)

- Participants who require delay of nivolumab should be re-evaluated weekly or more frequently if clinically indicated and resume nivolumab dosing when re-treatment criteria are met.

Rescheduling:

- Nivolumab may be delayed until the next planned ipilimumab dose if the next ipilimumab dose is scheduled within the next 12 days. This will permit periodic ipilimumab dosing to be synchronized with nivolumab dosing.

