# 7.1.1.3 Immune-Mediated Adverse Events (US Submission)

In order to further characterize AEs of special clinical interest, analysis of immune-mediated AEs (IMAE) will be conducted. IMAEs are specific events (or groups of PTs describing specific events) that include pneumonitis, diarrhea/colitis, hepatitis, nephritis/renal dysfunction, rash, endocrine (adrenal insufficiency, hypothyroidism/thyroiditis, hyperthyroidism, diabetes mellitus, and hypophysitis), and other specific events, considered as potential immune-mediated events by investigator that meet the definition summarized below:

- those occurring within 100 days of the last dose,
- regardless of causality,
- treated with immune-modulating medication (of note, endocrine AEs such as adrenal insufficiency, hypothyroidism/thyroiditis, hyperthyroidism, diabetes mellitus, and hypophysitis are considered IMAEs regardless of immune-modulating medication use, since endocrine drug reactions are often managed without immune-modulating medication).
- with no clear alternate etiology based on investigator assessment, or with an immune-mediated component

The list of MedDRA preferred terms used to identify IMAEs is revisited quarterly and updated accordingly. The preferred terms used for the selection at the time of the database lock by categories will be provided.

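### The SAP's re-challenge rule counts any infusion after IMAE onset, so participants dosed on schedule through an event are pooled with those held and restarted

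*SAP*

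**What the plan says.** SAP 7.6.7 applies the rule to a defined population, "for all nivolumab treated subjects who experienced at least one IMAE". The first output is "Summary of subjects who were re-challenged with nivolumab by IMAE category, with extended follow-up"; the second is the same summary for re-exposure to either drug. The rule for both is that "re-challenge is considered to have occurred when last nivolumab and/or ipilimumab infusion was administered after the onset of an IMAE". The section asks for no recurrence rate, no comparison, and no split of these two summaries by grade or by whether a dose was held.

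SAP 7.1.1.3 decides which events are IMAEs. Non-endocrine events must have been "treated with immune-modulating medication (of note, endocrine AEs such as adrenal insufficiency", while endocrine events "are considered IMAEs regardless of immune-modulating medication use". IMAEs count whatever the causality, provided there is no clear alternative cause or there is an immune-mediated component.

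Protocol 4.5.2.1 sets the delay rules for Arm A: "Dose delay criteria apply for all drug-related AEs". The listed triggers include "Grade 2 non-skin, drug-related AE, with the exception of fatigue" and "Grade 3 skin, drug-related AE". The investigator may also delay for any other event on judgement.

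**The concern.** In ordinary use, re-challenge means that treatment was stopped because of a toxicity and then started again. The protocol treats that as a distinct situation: Sections 4.5.4.1 and 4.5.4.2 set conditions for resuming each drug after a delay. The SAP rule does not identify that group. It identifies everyone who had at least one infusion after onset, including participants whose schedule never changed.

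At stake is the reading of one safety presentation for the US submission. A reader who wants to know what happened when dosing was restarted after, say, a rash or a thyroid event will find a larger group than the label suggests, with no way inside the table to separate the two kinds of exposure.

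**Working it through.** The plan states no figure for re-challenge, so there is nothing to reproduce. The check is one of logic.

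**Step 1. What the rule requires.** The last infusion falls after onset if, and only if, at least one infusion falls after onset. The rule is therefore 'any infusion after onset'. A participant given one scheduled dose shortly after onset and then stopped for good also meets it.

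**Step 2. Which IMAEs can be dosed through without a delay.** Setting SAP 7.1.1.3 beside Protocol 4.5.2.1:

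- *Endocrine, Grade 1:* an IMAE even if untreated; below the Grade 2 non-skin trigger. On-schedule dosing is allowed.
- *Rash, Grade 1-2:* an IMAE only if given immune-modulating medication; below the Grade 3 skin trigger. On-schedule dosing is allowed.
- *Other non-endocrine, Grade 1:* an IMAE only if so treated; below the Grade 2 trigger. On-schedule dosing is possible.
- *Judged not drug-related:* can still be an IMAE, but the delay criteria are written for drug-related events. On-schedule dosing is possible. The requirement on alternative cause in SAP 7.1.1.3 should narrow this group.
- *Drug-related Grade 2 or higher non-skin, or Grade 3 or higher skin:* the protocol calls for a delay or, for some events, discontinuation. Someone with such an event who is later dosed would normally be a genuine restart.

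The first four groups and the restarts in the fifth all satisfy the SAP rule.

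**Step 3. Whether another output separates them.** SAP 7.6.7 tabulates IMAEs leading to dose delay or reduction, and SAP 7.4.2.1 summarises delays and their reasons. Neither is cross-classified with re-challenge. Presentation by category keeps a thyroid event out of the pneumonitis row, but does not separate held from continued participants within a row.

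**Step 4. Effect on the count.** Number labelled re-challenged = (held and restarted) + (dosed after onset with no delay for that event). The inflation equals the second term. The documents give no value for it.

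**Step 5. Effect on any recurrence figure a reader might derive.** Let w be the share who continued without a delay, r_c their recurrence risk, and r_h the risk in those held and restarted. Then

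pooled risk = w × r_c + (1 − w) × r_h, so the shift from r_h is w × (r_c − r_h).

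None of the three is in the documents. Purely as assumptions, take r_h = 30% and w = 25%, 50%, 75%:

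- r_c = 10%: pooled 25%, 20%, 15%
- r_c = 30%: pooled 30% throughout
- r_c = 50%: pooled 35%, 40%, 45%

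Over this range the shift runs from 0.75 × (10 − 30) = −15 points to 0.75 × (50 − 30) = +15 points. The sign depends wholly on whether r_c is below or above r_h.

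**The case against.** The strongest reply has four parts.

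*The rule is explicit and reproducible, and it measures re-exposure after onset.* This stands. It is also why replacing the definition outright would be a mistake: a participant whose treated event resolved between two-weekly doses, or who was dosed within the 3-day tolerance, was genuinely re-exposed but would drop out of a rule that required a delay.

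*The pooling is narrow.* This largely stands. A reader might infer that every mild immune event dosed through is swept in, but the documents do not support that. An untreated mild non-endocrine event is not an IMAE. Under Protocol 4.5.4.1 and 4.5.4.2, systemic steroids given for a drug-related toxicity must be stopped or tapered to a low dose before dosing resumes, and drug-related pulmonary toxicity, diarrhoea or colitis must be back to baseline. The by-category layout also confines the mixing. What remains is mixing within a category, most plainly in the endocrine categories and rash.

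*Held cases can be traced elsewhere.* In part. The delay tables and the by-subject IMAE and dosing listings would let someone reconstruct the split by hand. The SAP does not plan to do it.

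*The table shells may already split the summary.* SAP Section 9 places the mock-ups in a Data Presentation Plan that is not among the documents, so this cannot be excluded. The SAP text, which defines the term, does not ask for it.

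**Conclusion.** The point holds as a matter of definition and labelling. SAP 7.6.7 calls participants re-challenged whose treatment was never interrupted, and nothing in the protocol or SAP separates them from those held and restarted. Two consequences follow whenever such participants exist: the count under that label is too large for its ordinary meaning, and the summary cannot show what followed a restart.

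A reader might go further and infer that the pooling dilutes the recurrence risk and so gives false reassurance on safety. The documents do not support this. The SAP plans no recurrence estimate, gives no recurrence rates, and offers no basis for assuming that participants who continued recur less often than those restarted; Step 5 shows that either sign is possible.

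The importance is low. Two descriptive summaries are affected, and no tested endpoint, alpha or sample size depends on them. The conclusion assumes that at least some participants were dosed without delay after an IMAE. The protocol's rules permit this, but the documents do not count them.

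**What to change.** In SAP 7.6.7, keep both summaries of exposure after IMAE onset, with the present rule as the entry condition, and divide each into:

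- (a) dosing resumed after a dose was delayed for that IMAE, identified by the adverse-event action code for a delayed drug (SAP 7.1.1) or by a delay of more than 3 days with that reason on the dosing pages (SAP 7.4.2.1);
- (b) dosing continued without such a delay.

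Show each by worst grade within IMAE category, and reserve the term re-challenge for (a). No one is dropped: re-exposure without a qualifying delay is reported under (b).

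One derivation detail needs settling. Protocol 4.5.2.1 allows a dose held for an adverse event to be skipped, whereas SAP 7.4.2.5 treats omissions as not permitted and gives no derivation. The flag's specification should say where a skipped dose falls.

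The cost is one derived flag from data already collected, a change of SAP wording and table shell, and smaller cells in some categories. No new data collection, protocol amendment or change to clinical management is involved.

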# 7.6.8 Other Events of Special Interest

OEOSI will be summarized by treatment group for each category.

The following analyses will be conducted using the 100-day safety window:

- Overall summary of OEOSI by worst CTC grade (any grade, grade 3-4, grade 5) presented by Category / PT
- Overall summary of drug-related OEOSI by worst CTC grade (any grade, grade 3-4, grade 5) presented by Category / PT

A by-subject listing of OEOSI will be provided.

# 7.6.9 Multiple Events

The following summary tables will be provided:

- A table showing the total number and rate (exposure adjusted) of occurrences for all AEs.
- A table showing the total number and rate (exposure adjusted) of occurrences for AEs occurring in at least 5% of subjects in any treatment group.

In addition, the rate (exposure adjusted) and its 95% CI evaluated for different time intervals will be displayed graphically for each treatment group. This analysis will be limited to the rate of all AEs and all drug-related AEs. The analyses will be conducted using the 30-day safety window.

A listing displaying the unique instances of all AEs, i.e., after duplicates have been eliminated and overlapping and contiguous occurrences of the same event (i.e. same PT) have been collapsed will be provided. No formal comparisons will be made between treatment groups.

# 7.6.10 Laboratory Parameters

The analysis population for each laboratory test is restricted to treated subjects who underwent that laboratory test. Laboratory tests (in addition to the tests specified below) with CTC criteria collected in the specific studies may also be included in the summaries.

# 7.6.10.1 Hematology

The following will be summarized by treatment group as worst CTC grade on-treatment per subject and as shift table of worst on-treatment CTC grade compared to baseline CTC grade per subject: hemoglobin (HB), platelets, white blood counts (WBC), absolute neutrophils count (ANC) and lymphocyte count (LYMPH).

The analyses will be conducted using the 30-day safety window.

A by-subject listing of these laboratory parameters will be provided.

# 7.6.10.2 Serum Chemistry

The following will be summarized by treatment group as worst CTC grade on-treatment per subject and as shift table of worst on-treatment CTC grade compared to baseline CTC grade per subject: ALT, AST, alkaline phosphatase (ALP), total bilirubin and creatinine.

The analyses will be conducted using the 30-day safety window.

A by-subject listing of these laboratory parameters will be provided.

# 7.6.10.3 Electrolytes

The following will be summarized by treatment group as worst CTC grade on-treatment per subject and as shift table of worst on-treatment CTC grade compared to baseline CTC grade per subject: sodium (high and low), potassium (high and low), calcium (high and low), magnesium (high and low), and Glucose Serum (fasting hyperglycemia and hypoglycemia regardless of fasting status)

The analyses will be conducted using the 30-day safety window.

A by-subject listing of these laboratory parameters will be provided.

# 7.6.10.4 Additional Analyses

In addition, further analyses on specific laboratory parameters will be performed by treatment group:

#### Abnormal Hepatic Function Test

The number of subjects with the following laboratory abnormalities from on-treatment evaluations will be summarized by treatment group:

- ALT or AST > 3 x ULN, > 5 x ULN, > 10 x ULN and > 20 x ULN
- Total bilirubin > 2 x ULN
- Concurrent (within 1 day) ALT or AST > 3 x ULN and total bilirubin > 2 x ULN
- Concurrent (within 30 days) ALT or AST > 3 x ULN and total bilirubin > 2 x ULN

The analyses will be conducted using the 30-day safety window.

A by-subject listing of these specific abnormalities will be provided.

#### Abnormal Thyroid Function Test

The number of subjects with the following laboratory abnormalities from on-treatment evaluations will be summarized by treatment group:

- TSH value > ULN and
  - with baseline TSH value ≤ ULN
  - with at least one FT3/FT4 test value < LLN within 2-week window after the abnormal TSH test

  - with all FT3/FT4 test values ≥ LLN within 2-week window after the abnormal TSH test
  - with FT3/FT4 missing within 2-week window after the abnormal TSH test.

#### • TSH < LLN and

- with baseline TSH value ≥ LLN
- with at least one FT3/FT4 test value > ULN within 2-week window after the abnormal TSH test
- with all FT3/FT4 test values ≤ ULN within 2-week window after the abnormal TSH test
- with FT3/FT4 missing within 2-week window after the abnormal TSH test

The analyses will be conducted using the 30-day safety window.

A by-subject listing of these specific abnormalities will be provided.

#### 7.6.11 Vital Signs and Pulse Oximetry

Vital signs and pulse oximetry (i.e. % oxygen saturation) collected on the CRF will be provided in separate listings.

#### 7.6.12 Physical Measurements

Physical measurements will be listed by subject.

#### 7.6.13 Non-Protocol Medical Procedures

Non-protocol medical procedures will be listed by subject.

# 7.6.14 Immunogenicity Analysis

Further details on immunogenicity background and rationale, definitions, population for analyses and endpoints are described in APPENDIX 3.

#### **Incidence of ADA**

Number (%) of subjects will be reported for the following parameters based on Evaluable Subjects.

- Baseline ADA-positive
- ADA-positive
  - Persistent Positive (PP)
  - Not PP-Last Sample Positive
  - Other positive
  - Neutralizing Positive
- ADA-negative

A listing of all ADA assessments will be provided.

A spider plot of nivolumab ADA test result (titers) over time may be provided for nivolumab ADA positive subjects.

#### The effect of ADA on safety and efficacy

- Summary of Select Adverse Events of Hypersensitivity/Infusion Reaction by ADA Status (Positive, Negative)
- Swimmer plot of occurrence of ADA and NAb Occurrence in Relation to PFS, BOR per BICR and OS

# 7.6.15 Pregnancy

A by-subject listing of pregnancy tests results will be provided for randomized female subjects.

#### 7.6.16 Adverse Events by Subgroup

Overall summary of any AEs and drug-related AEs by worst CTC grade (any grade, grade 3-4, grade 5) presented by SOC/PT and for each treatment group for the following subgroups:

- Sex (Male vs. Female)
- Race
- Age  $(< 65 \text{ vs. } 65 < 75 \text{ vs. } 75 < 85 \text{ vs. } \ge 85 \text{ vs. } \ge 75 \text{ vs. } \ge 65)$
- Region (North America vs. EU vs. Asia vs. ROW)
- Prior chemotherapy status (Yes/No)

These analyses will be conducted using the 30-day safety window only.

#### 7.7 Pharmacokinetics

The nivolumab/ipilimumab concentration data obtained in this study will be combined with data from other studies in the clinical development program to develop a population PK model. This model will be used to evaluate the effects of intrinsic and extrinsic covariates on the PK of nivolumab/ipilimumab. In addition, exposure-response analyses with selected efficacy and safety endpoints may be conducted. Results of population PK and exposure response-analyses will be reported separately if conducted.

#### 7.8 Biomarkers

Analyses for Biomarkers such as PD-L1 CPS, PD-L1 TPS, Gene Expression Profile (GEP) and Tumor Mutation Burden (TMB) are described below.

#### 7.8.1 Distribution of PD-L1 CPS

Descriptive statistics of PD-L1 CPS:

- Listing of all PD-L1 IHC data, all PD-L1 tested subjects.
- Summary of tumor specimen acquisition and characteristics, all randomized subjects.
- Summary statistics of PD-L1 CPS in all randomized subjects with quantifiable PD-L1 CPS.
- Summary of BOR and ORR by baseline PD-L1 CPS in all randomized subjects.
- Cumulative distribution plot of baseline PD-L1 CPS versus population percentile in all randomized subjects with quantifiable PD-L1 CPS.
- Box plots of PD-L1 CPS versus Response Status (BICR assessment) in all randomized subjects with quantifiable PD-L1 CPS.
- Waterfall plot of Individual PD-L1 CPS in all randomized subjects with quantifiable PD-L1 CPS.
- Histogram of the distribution of PD-L1 CPS.

# 7.8.2 Association Between PD-L1 CPS and Efficacy

Analyses of association between PD-L1 CPS at baseline and efficacy measures will be performed for scheduled formal efficacy analyses in the study. The analysis population will be among all randomized subjects unless otherwise specified.

For each PD-L1 CPS subgroup (further specified in the DPP) at baseline:

- OS/PFS curves for each treatment group will be estimated using the Kaplan-Meier product limit method. Two-sided, 95% confidence intervals for median OS/PFS will be constructed based on a log-log transformed CI for the survivor function S(t).
- Forest plot of Hazard Ratios with 95% CIs
- Frequency and percentage of BOR per BICR will be summarized for each treatment group.
- ORR will be computed by treatment group along with exact 95% CIs using the Clopper Pearson method.

The following analysis will be performed to evaluate the association between PD-L1 CPS level and BICR-determined PFS (per primary definition) or OS.

- An exploratory Cox proportional hazards model will be fitted for PFS per BICR or OS with PD-L1, treatment arm and PD-L1 treatment arm interaction, among All PD-L1 Evaluable Subjects. An appropriate transformation of PD-L1 CPS may be considered depending on an assessment of fit of the model.
- A plot of estimated log(hazard ratio) with 95% confidence band vs PD-L1 CPS > 0 (X-axis)

The following analysis will be performed to evaluate the evaluation of association between PD-L1 CPS level and ORR (per BICR) among PD-L1 CPS evaluable subjects for each treatment arm.

- A logistic regression model will be fitted for ORR with PD-L1 CPS among all PD-L1 evaluable subjects. An appropriate transformation of PD-L1 CPS may be considered depending on an assessment of fit of the model.
- A plot of estimated response probability with 95% confidence band vs PD-L1 CPS (X-axis)
- Box plot of PD-L1 CPS versus Response Status

Receiver Operating Characteristics (ROC) analysis with ORR (per BICR) will be performed to help assess in-study predictive accuracy of the logistic regression model and whether there is a clinically meaningful threshold of PD-L1 CPS. A plot of the ROC curve and a plot of estimated Youden's index vs PD-L1 CPS will be provided for all PD-L1 CPS evaluable subjects.

